13.2 Funding and financial disclosure

Funding

This study will be funded by its sponsor.

Financial disclosure

Each investigator (including principal and/or any sub investigators) who is directly involved in the treatment or evaluation of research subjects has to provide a financial disclosure according to all applicable legal requirements. All relevant documentation will be filed in the trial master file.

13.3 Ethical and legal conduct of the study

The procedures set out in this protocol, pertaining to the conduct, evaluation, and documentation of this study, are designed to ensure that the sponsor and investigator abide by Good Clinical Practice (GCP) guidelines and the guiding principles detailed in the

Declaration of Helsinki. The study will also be carried out in keeping with applicable local law(s) and regulation(s).

Documented approval from appropriate IEC(s)/IRBs will be obtained for all participating centers/countries before start of the study, according to GCP, local laws, regulations and organizations. When necessary, an extension, amendment or renewal of the IEC/IRB approval must be obtained and forwarded to the sponsor. Upon request, the responsible unit (e.g., IEC/IRB, head of the study center/medical institution) must supply the sponsor with a list of the IEC/IRB members involved in the vote, and a statement confirming that the IEC/IRB is organized and operating according to GCP and applicable laws and regulations.

Strict adherence to all specifications laid down in this protocol is required for all aspects of study conduct; the investigator may not modify or alter the procedures described in this protocol.

Modifications to the study protocol will not be implemented by either the sponsor or the investigator without agreement by both parties. However, the investigator or the sponsor may implement a deviation from, or a change of, the protocol to eliminate an immediate hazard(s) to the trial subjects without prior IEC/IRB/sponsor approval/favorable opinion. As soon as possible, the implemented deviation or change, the reasons for it and if appropriate the proposed protocol amendment should be submitted to the IEC/IRB/head of medical institution/ sponsor. Any deviations from the protocol must be explained and documented by the investigator.

Details on discontinuation of the entire study or parts thereof can be found in Section 12.

13.4 Subject information and consent

All relevant information on the study will be summarized in an integrated subject information sheet and informed consent form provided by the sponsor or the study center. A sample subject information and informed consent form is provided as a document separate to this protocol.

Based on this subject information sheet, the investigator or designee will explain all relevant aspects of the study to each subject/legal representative or proxy consentor (if the subject is under legal protection), prior to his entry into the study (i.e., before any examinations and procedures associated with the selection for the study are performed or any study-specific data is recorded on study-specific forms).

The investigator will also mention that written approval of the IRB/IEC has been obtained.

Each subject/legal representative or proxy consentor will be informed about the following aspects of premature withdrawal:

- Each subject has the right to withdraw from the study at any time without any disadvantage and without having to provide reasons for this decision.
- The subject's consent covers end-of-study examinations as specified in the visit descriptions in Section 9.2 to be conducted after withdrawal of consent.
- The subject's data that have been collected until the time of withdrawal will be retained and statistically analyzed in accordance with the statistical analysis plan.
- Subject material obtained before withdrawal may be used to generate subject-specific data after withdrawal (e.g., image reading, analysis of biological specimen such as blood, urine or tissues); these data would also be retained and statistically analyzed in accordance with the statistical analysis plan. The subject has the right to object to the generation and processing of this post-withdrawal data. The subject's oral objection may be documented in the subject's source data.

Each subject/legal representative or proxy consentor will have ample time and opportunity to ask questions.

Only if the subject/legal representative or proxy consentor voluntarily agrees to sign the informed consent form and has done so, may he enter the study. Additionally, the investigator will personally sign and date the form. The subject/legal representative or proxy consentor will receive a copy of the signed and dated form.

The signed informed consent statement is to remain in the investigator site file or, if locally required, in the patient's note/file of the medical institution.

In the event that informed consent is obtained on the date that baseline study procedures are performed, the study record or subject's clinical record must clearly show that informed consent was obtained prior to these procedures.

For the optional pharmacogenetics testing, a separate informed consent will additionally be obtained according to the procedures described above.

1. If the subject is not capable of providing a signature, a verbal statement of consent can also be given in the presence of an impartial witness (independent of the sponsor and the investigator). This is to be documented by a signature from the informing physician as well as by a signature from the witness.
2. In emergency situations, when prior consent of the subject is not possible, the consent of the subject's legal representative(s) or proxy consentor, if present, should be requested. The subject should be informed about the study as soon as possible and his consent to continue the study should be requested.

The informed consent form and any other written information provided to subjects/legal representatives or proxy consentors will be revised whenever important new information becomes available that may be relevant to the subject's consent, or there is an amendment to the protocol that necessitates a change to the content of the subject information and/or the written informed consent form. The investigator will inform the subject/legal representative or proxy consentor of changes in a timely manner and will ask the subject to confirm his participation in the study by signing the revised informed consent form. Any revised written

informed consent form and written information must receive the IEC/IRB's approval/favorable opinion in advance of use.

13.5 Publication policy and use of data

The sponsor has made the information regarding the study protocol publicly available on the internet at www.clinicaltrials.gov.

All data and results and all intellectual property rights in the data and results derived from the study will be the property of the sponsor who may utilize them in various ways, such as for submission to government regulatory authorities or disclosure to other investigators.

Regarding public disclosure of study results, the sponsor will fulfill its obligations according to all applicable laws and regulations. The sponsor is interested in the publication of the results of every study it performs.

The sponsor recognizes the right of the investigator to publish the results upon completion of the study. However, the investigator, whilst free to utilize study data derived from his/her center for scientific purposes, must obtain written consent of the sponsor on the intended publication manuscript before its submission. To this end, the investigator must send a draft of the publication manuscript to the sponsor within a time period specified in the contract. The sponsor will review the manuscript promptly and will discuss its content with the investigator to reach a mutually agreeable final manuscript.

13.6 Compensation for health damage of subjects/insurance

The sponsor maintains clinical trial insurance coverage for this study in accordance with the laws and regulations of the country in which the study is performed.

15.1.1 Overview of changes to the study

Table of main changes

Section # & Name	Description of Change	Brief Rationale
3 Introduction	Text describing the product updated to include most recent data from the ongoing First in Man Phase 1 study	Update of data available for BAY 1093884
2 Synopsis 5 Study design 7.4.1 Selection of doses in the study	Dose escalation criteria and safety rules between cohorts added in addition to those already described within cohorts/subjects	Present a more detailed version of the study design
2 Synopsis 5 Study design 7.1.1 Prophylaxis treatment with BAY 1093884 7.4.1 Selection of doses in the study 7.4.1.1 PK/PD criteria for dose recommendations 9.6.1.7 Adverse events requiring an ad hoc DMC meeting 13.1.2 External bodies	Text added providing further detail on the role and responsibilities of the DMC	Clearly describe the safety oversight and decision process of the DMC
5 Study design	Text added describing the rationale for fixed doses	Provide justification for change from weight-based doses to fixed doses
5 Study design	Communication plan added	Description of methods for communicating safety data and dose escalation decisions to investigator sites
6.3.2 Replacement	Text added stating that subjects may be replaced only if they have not withdrawn from the study for drug-related safety concerns	Clarification of description of when subjects may be replaced.

Integrated Clinical Study Protocol
BAY 1093884 / 19580

05 APR 2019

Version 4.0

Page: 89 of 96

Section # & Name	Description of Change	Brief Rationale
7.1.2 Treatment of bleeds 8.1 Prior and concomitant therapy (including treatment of bleeds)	Guidance added for use of bypassing agents to treat bleeds during treatment with BAY 1093884	Intensity and location of trauma for which bleeding has not yet occurred must be considered by investigator prior to initiating preventative treatment with a replacement factor or bypassing agent.
7.1.3 Treatment of PK/PD assessments 8.2 Post-study therapy 9.1 Tabular schedules of evaluations 9.2.1.10 Every 12 weeks visit (\pm 7 days calculated from Visit 2) 9.2.2.15 Every 12 weeks visit (\pm 7 days calculated from Visit 2)	Every 24-week visit changed to frequency of every 12 weeks	Additional safety monitoring of subjects
7.2 Identity of study treatment	Dose strength changed from “100 mg/mL” to “either 100 mg/mL or 150 mg/mL”	Introduction of 150 mg/mL dose strength
7.4.1.1 PK/PD criteria for dose recommendations	Additional detail provided on the amount and type of safety, PK and PD data collected	Further describe the amount of safety, PK and PD data collected in order to open next dose cohort
9.2.1 Visit description for non-PK subjects 9.2.2 Visit description for PK subjects	Local ECG added at Visits 3 – 7 and every 12 week visits	Additional safety monitoring
9.2.1.3 Visit 2 – Start of BAY 1093884 treatment at the respective dose (\leq 6 weeks after Visit 1) 9.2.2.3 Visit 2.1 – Start of BAY 1093884 treatment at the respective dose (\leq 6 weeks after Visit 1) and 1st PK day 0	LDL added to blood samples collected at Visit 2	Additional safety laboratory collection
9.6.1.2.2 Intensity	AE intensity should be graded according to NCI CTCAE version 5.0	Updated guidance for the assessment of AEs
9.6.1.5 Reporting of medical device failures	Section added describing reporting of non-approved medical device failures	Guidance specific to Japan sites for reporting of non-approved medical device failures

Integrated Clinical Study Protocol
BAY 1093884 / 19580

05 APR 2019

Version 4.0

Page: 90 of 96

Section # & Name	Description of Change	Brief Rationale
9.6.1.6 Dose-limiting toxicities	Section added to define DLTs for the study	Additional safety guidance on the reporting of DLTs
9.6.3.1 Clinical laboratory assessments	Lactate dehydrogenase and fibrinogen added to standard safety laboratory analyses	Additional safety laboratory blood samples
9.6.3.1 Clinical laboratory assessments	Immunoglobulins will be collected for hypersensitivity reactions	Addition of immunoglobulins to blood tests collected for hypersensitivity reactions
9.6.3.1 Clinical laboratory assessments	LDH added to central laboratory tests for thromboembolic and thrombotic microangiopathic events	Additional safety laboratory collection
9.6.3.4 Electrocardiogram	Section added to note that ECGs will be performed at PK visits	Description of ECG safety assessment schedule
2 Synopsis 10.3 Variables and planned statistical analyses	Injection site reactions removed as separate endpoint, as these will be collected as part of regular AE reporting	Remove redundant endpoint of injection site reaction
12 Premature termination of the study	Note pertaining to DMC review of thromboembolic or thrombotic microangiopathic events removed, as this is now described in new section 9.6.1.7	Remove redundant DMC review text regarding thromboembolic or thrombotic microangiopathic events

Table of corrections and clarifications

Section # & Name	Description of Change
6.1 Inclusion criteria	Inclusion criteria 1 and 2 combined into one criterion, as subjects cannot satisfy both criteria. Content of criteria not changed.
2 Synopsis 6.2 Exclusion criteria	Exclusion criterion 12 text updated to clarify that patients receiving treatment with an investigational drug 3 months prior to the screening visit are excluded.
6.3.1 Withdrawal 10.5 Planned interim analysis	Definition of completer updated to specify that at least one Part B segment must be completed by the subject.
7.1.1 Prophylaxis treatment with BAY 1093884	Frequency of administration updated from “once weekly” to “every 7 days ± 1 day” for consistency with description of visit schedule.
8.1 Prior and concomitant therapy (including treatment of bleeds)	Wording simplified to state that no immunomodulatory drugs are allowed during the study.

Section # & Name	Description of Change
Table 9-2B Table 9-3B	Part B and subsequent visits combined into one column, as procedures are identical at these visits
Table 9-2A Table 9-2B 9.2.1.1 Visit 1 – Screening visit Table 9-3A Table 9-3B 9.3.5 Pharmacogenetic testing – optional	Clarification that pharmacogenetic sample may be collected at any time point during the study once separate consent is obtained, not just Visit 1
9.4 Efficacy	CCI efficacy variable of primary interest clarified to note that the number of subjects in each 12-week Part B period, as opposed to Part B overall, will be observed
10.1 General considerations 10.3.3 Analysis of efficacy	Description of Part B clarified to note that there are multiple 12-week periods after Part A
10.3.3 Analysis of efficacy	Sentence added: “It should be noted that this kind of analysis must be interpreted carefully, as the restriction is based on post-baseline events.”

Typographical, grammatical, and other minor edits are not identified.

15.1.2 Changes to the protocol text

Changes to the protocol text are provided in a separate track changes version.

15.2 Amendment 5

Integrated protocol Version 3.0, dated 12 FEB 2019

15.2.1 Overview of changes to the study

Table of main changes

Section # and name	Description of change	Brief rationale
Table 9-1 Visit schedule overview	The visit schedule was updated to include an additional safety visit 6 weeks (\pm 1 day) after dose escalation.	This change will allow for additional safety monitoring of study subjects after escalation to a higher dose.
Table 9-2 Tabular schedule of assessments (subjects not participating in PK evaluations; Screening and Part A)		
Table 9-3 Tabular schedule of assessments (subjects not participating in PK evaluations; Part B through end of study)		

Integrated Clinical Study Protocol
BAY 1093884 / 19580

05 APR 2019

Version 4.0

Page: 92 of 96

Section 9.2.1.8 Visit 6 (12 weeks \pm 1 day after Visit 2) assessment of dose escalation

Section 9.2.1.11 Additional safety visits after dose escalation (if applicable)

Table 9-5 Tabular schedule of assessments (subjects participating in PK evaluations; Part B through end of study)

Section 9.2.2.13 Visit 6.4 – 2nd PK Day 7 (168 h) and assessment of dose escalation

Section 9.2.2.16 Additional safety visits after dose escalation (if applicable)

Section 2 Synopsis Section 6.1 Inclusion criteria	Inclusion criterion 1 was modified to specify that subjects with inhibitors against FVIII or FIX also have undetectable FVIII or FIX levels.	DMC recommendation
--	--	--------------------

Section 2 Synopsis Section 6.2 Exclusion criteria	Exclusion criterion 10 was modified to more accurately describe advanced liver disease.	DMC recommendation
--	---	--------------------

Table of corrections and clarifications

Section # & Name	Description of Change
3 Introduction	The portion of the section presenting information on the product was updated to refer the reader to the “current version of the IB” instead of version 3.
7.2 Identity of study treatment	Vial size was corrected from 2 mL to 10 mL. The contents of the 150 mg/mL vial were corrected from 1.6 mL to 1.8 mL of BAY 1093884.
9.2.1.11 Additional safety visits after dose escalation (if applicable)	The ECG erroneously omitted in amendment 4 was added to the description of the additional safety visit.
9.2.2.9 Phone call (3 weeks \pm 2 days after Visit 5)	The time window of the phone call at Week 9 was corrected from \pm 1 day to \pm 2 days.
9.6.3.1 Clinical laboratory assessments	The unit of measure for FVIII/FIX testing was corrected from BU to BU/mL.

Typographical, grammatical, and other minor edits are not identified.

15.2.2 Changes to the protocol text

Changes to the protocol text are provided in a separate track changes version.

16. Appendices

16.1 Hemophilia Joint Health Score

Integrated Clinical Study Protocol
BAY 1093884 / 19580

05 APR 2019

Version 4.0

Page: 95 of 96

Subject ID #: _____

Name of Physiotherapist: _____

Assessment # : _____

Date: _____

Time: _____

yyyy / mm / dd

Hemophilia Joint Health Score 2.1 - Summary Score Sheet

	Left Elbow	Right Elbow	Left Knee	Right Knee	Left Ankle	Right Ankle
Swelling	 NE	 NE	 NE	 NE	 NE	 NE
Duration (swelling)	 NE	 NE	 NE	 NE	 NE	 NE
Muscle Atrophy	 NE	 NE	 NE	 NE	 NE	 NE
Crepitus on motion	 NE	 NE	 NE	 NE	 NE	 NE
Flexion Loss	 NE	 NE	 NE	 NE	 NE	 NE
Extension Loss	 NE	 NE	 NE	 NE	 NE	 NE
Joint Pain	 NE	 NE	 NE	 NE	 NE	 NE
Strength	 NE	 NE	 NE	 NE	 NE	 NE
Joint Total						

Sum of Joint Totals

+

NE = Non-Evaluable

Global Gait Score

+

(NE included in Gait items)

HJHS Total Score

=

Swelling

- 0 = No swelling
- 1 = Mild
- 2 = Moderate
- 3 = Severe

Crepitus on Motion

- 0 = None
- 1 = Mild
- 2 = Severe

Strength (Using The Daniels & Worthingham's scale)

Within available ROM

- 0 = Holds test position against gravity with maximum resistance (gr.5)
- 1 = Holds test position against gravity with moderate resistance (but breaks with maximal resistance) (gr.4)
- 2 = Holds test position with minimal resistance (gr. 3+), or holds test position against gravity (gr.3)
- 3 = Able to partially complete ROM against gravity (gr.3-/2+), or able to move through ROM gravity eliminated (gr.2), or through partial ROM gravity eliminated (gr.2-)
- 4 = Trace (gr.1) or no muscle contraction (gr.0)

NE = Non-evaluable

Duration

- 0 = No swelling or < 6 months
- 1 = ≥ 6 months

Flexion Loss

- 0 = < 5°
- 1 = 5° - 10°
- 2 = 11° - 20°
- 3 = > 20°

Muscle Atrophy

- 0 = None
- 1 = Mild
- 2 = Severe

Extension loss (from hyperextension)

- 0 = < 5°
- 1 = 5° - 10°
- 2 = 11° - 20°
- 3 = > 20°

Global Gait (walking, stairs, running, hopping on 1 leg)

- 0 = All skills are within normal limits
- 1 = One skill is not within normal limits
- 2 = Two skills are not within normal limits
- 3 = Three skills are not within normal limits
- 4 = No skills are within normal limits

NE = Non-evaluable

Joint Pain

- 0 = No pain through active range of motion
- 1 = No pain through active range; only pain on gentle overpressure or palpation
- 2 = Pain through active range

NOTE: There is an accompanying instruction manual and worksheets that are required when administering the HJHS

General Comments:

Integrated Clinical Study Protocol
BAY 1093884 / 19580

05 APR 2019

Version 4.0

Page: 96 of 96

The HJHS is designed for use by physiotherapists. In order to maintain the precision and validity of the tool (score), the developers of the tool strongly recommend that the tool be used by physiotherapists/healthcare professionals who have hemophilia-related expertise/experience and have been trained in the use of clinical measures, musculoskeletal assessment and specifically administration of the HJHS.

It is essential for the physiotherapist to possess the required expertise and skills necessary to use anthropometric measures such as muscle testing and range of motion /goniometry, as well as posture & gait assessment prior to performing the evaluation (HJHS).

Document Type:	Statistical Analysis Plan
Official Title:	Multiple escalating dose study of BAY 1093884 in adults with hemophilia A or B with or without inhibitors
NCT Number:	NCT03597022
Document Date:	10-MAR-2020

Title page

Study Protocol Title (incl. version no. and date): Multiple escalating dose study of BAY 1093884 in adults with hemophilia A or B with or without inhibitors, Version 2.0, dates 26 Jun 2018

SAP (incl. Version no. and date): 1.0, dated 23 Jul 2018

Analysis purpose: Post-hoc analyses

Clinical study phase: 2 **Date:** 10 MAR 2020

Study No.: 19580 **Version:** 1.0

Author: PPD

Confidential

The information provided in this document is strictly confidential and is intended solely for the guidance of the clinical investigation. Reproduction or disclosure of this document, whether in part or in full, to parties not associated with the clinical investigation or its use for any other purpose without the prior written consent of the sponsor is not permitted.

Throughout this document, symbols indicating proprietary names (®, TM) are not displayed unless quotations from other documents are given. Hence, the appearance of product names without these symbols does not imply that these names are not protected.

This "Additional Statistical Analysis Plan" is produced on a word-processing system and bears no signatures.

**Additional Statistical Analysis Plan
for abbreviated CSR**

Preamble

This Statistical analyses plan is for the documentation of post-hoc analyses for publishing purposes.

Table of Contents

Title page.....1

1. Annualized Bleeding rates.....3

2. Individual Lab plot3

3. PK/PD individual plots3

1. Annualized Bleeding rates

The number of bleeds and annualized bleeding rate is shown by treatment arm. The table differentiates the bleeds into all bleeds and spontaneous bleeds. In addition, these bleeds are separated by treated and untreated bleeds. For the number of bleeds the 24 hours rule as well as the 72 hours rule as described in SAP sections 4.5.3 and 4.5.4 apply. Use SAS code from Kovaltry and/or Jivi as reference.

The annualized bleeding rate is defined as

$$\frac{(\# \text{ of bleeds in data scope time}) \cdot 365.25}{(\text{last date in data scope} - \text{first date in data scope} + 1)}$$

The following data scopes will be analysed:

- Bleeds in 6 months before randomization. The last date of data scope is the day of randomization, the first date in data scope is 6 months before, i.e. the time in the data scope is fixed at 183 days. This bleeds will be shown by dose initially received.
- Dose initially given: First date in that data scope is defined as first intake of the study treatment. Last date is the date of the intake of any study drug. Show bleeds for combined Part A and Part B (whole study time), as well as for Part A (last date is the end of Part A in this case) and Part B (first date is the start of Part B in this case).
- Dose actually given: show for the dose actually given the annualized bleeding rates in Part B - for patients that get escalated in Part B the last date in the data scope for a specific dose is the day the escalation into the higher dose group. For these patients the first day is the new dose group is the first date of the data scope for Part B and that escalated dose group is the day of the escalation.

Subgroup analyses will be performed by previous treatment.

2. Individual Lab plot

Show table CLIPS LB1C and figure CLIPS LB-F2 for available laboratory parameter and subjects.

3. PK/PD individual plots

Show figure CLIPS PK-F2 for available PK/PD parameter.

Title page**Multiple escalating dose study of BAY 1093884 in adults with hemophilia A or B with or without inhibitors****Bayer study drug** BAY 1093884**Clinical study phase:** 2 **Date:** 23 Jul 2018**Study No.:** 19580 **Version:** 1.0**Author:** PPD **Confidential**

The information provided in this document is strictly confidential and is intended solely for the guidance of the clinical investigation. Reproduction or disclosure of this document, whether in part or in full, to parties not associated with the clinical investigation or its use for any other purpose without the prior written consent of the sponsor is not permitted.

Throughout this document, symbols indicating proprietary names (®, TM) are not displayed. Hence, the appearance of product names without these symbols does not imply that these names are not protected.

This Statistical Analysis Plan is produced on a word-processing system and bears no signatures.

The approval of the Statistical Analysis Plan is documented in a separate Signature Document.

Table of Contents

Title page.....1

Abbreviations.....3

1. Introduction3

2. Study Objectives.....6

3. Study Design6

4. General Statistical Considerations9

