4.5.2 Annualized bleed rate

Regarding the definition on the annualized bleed rate (see section 6.2.1) the following datetime will be used:

For annualized bleed rate for Part A, the first datetime of Part A will be the datetime of the first administration of study drug (Visit 2 – Start of BAY 1093884 treatment at the respective dose). The last datetime of Part A will be 1 minute before the datetime of the Visit 6 administration of study drug (the first administration of study drug in Part B). For subjects who discontinue the study during Part A, the last datetime of Part A is the datetime of the later of last visit and last administration of study drug.

For annualized bleed rate for each 12-week Part B period, the first datetime of the Part B period will be the datetime of the first administration of study drug in Part B (Visit 6) in case of first Part B period, or the datetime of the administration of study drug of Visit 7 or any subsequent 12-week visit. The last datetime of Part B will be 1 minute before the datetime of the administration of study drug of Visit 7 or the following subsequent 12-week visit. For subjects who discontinue the study during Part B, the last datetime of Part B is the datetime of the later of last visit and last administration of study drug.

For annualized bleed rate for period on dose initially received (DIR), the first datetime on DIR will be the datetime of the first administration of study drug (Visit 2 – Start of BAY 1093884 treatment at the respective dose). The last datetime on DIR will be 1 minute before the datetime of the administration of the next higher dose of study drug (Visit 6 or Visit 7). For subjects who discontinue prior to administration of the next higher dose or never met the dose-escalation criteria, the last datetime on DIR is the datetime of the later of last visit and last administration of study drug.

4.5.3 24 hours rule

Count no more than 1 bleed in a calendar day. If there is more than 1 bleed in a calendar day, to determine the bleed that gets counted, give priority to treated bleeds, spontaneous or trauma bleeds, then joint bleeds. Otherwise, count the first bleed in the day. Severity and treatment response will come from this selected bleed. Bleed site will be aggregated over all bleeds from that day. Regardless of which bleed is selected, the time of the first bleed in the day will be used. All other infusions in the day for treating bleeds will be considered follow-up infusions.

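### Additional SAP bleeding rate by dose actually given: the escalation day counts under both doses, and a bleed on it can be counted twice

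*SAP*

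**What the plan says.** Section 1 of the Additional SAP (10 March 2020) divides the number of bleeds times 365.25 by last date minus first date plus one, so both end dates count as whole days. For the dose actually given in Part B, it states that "the last date in the data scope for a specific dose is the day the escalation into the higher dose group". A word is missing after 'day'. For the higher dose, "the first date of the data scope for Part B and that escalated dose group is the day of the escalation".

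From the main SAP (23 July 2018) it takes over only the two bleed-counting rules, sections 4.5.3 and 4.5.4. The first of these reads "Count no more than 1 bleed in a calendar day". It does not cite section 4.5.2, which sets period limits by date and time. There, for the dose initially received, "The last datetime on DIR will be 1 minute before the datetime of the administration of the next higher dose of study drug". Between the parts, "The last datetime of Part A will be 1 minute before the datetime of the Visit 6 administration of study drug".

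The Additional SAP also gives rows by dose initially given: Part A and B combined, and then "Part A (last date is the end of Part A in this case) and Part B (first date is the start of Part B" in turn. It does not define where Part A ends. For these rows it says "Last date is the date of the intake of any study drug", apparently meaning the last intake.

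**The concern.** On the natural reading, one calendar day is the last day on the old dose and the first day on the new one. With a formula that includes both ends, that day enters two denominators. A bleed on it falls inside both windows, and the text gives no rule for choosing one. The 24-hour rule limits bleeds per calendar day but does not allocate them between doses. Days, and possibly bleeds, summed over the dose rows would then exceed those observed. The main SAP had already closed this gap with its one-minute rule; the move to whole days reopened it in a table prepared for publication.

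The overlap concerns Cohort 1 and 2 subjects who escalate once Part B has begun, that is at Visit 7 or later. Cohort 3 cannot escalate.

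**Working it through.** The plan states no figure on this point, so there is none to reproduce. The check applies the Additional SAP formula to its own windows.

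**1. Days.** Example (assumed timing): Part B starts on day 0, escalation is on day 84 (12 weeks, SAP section 3), and the last dose is on day 161.
- Old dose: 84 − 0 + 1 = 85 days.
- New dose: 161 − 84 + 1 = 78 days.
- Sum: 85 + 78 = 163. Days observed: 161 − 0 + 1 = 162. The excess is one day.

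The old-dose denominator is too large by 1/84 = 1.2%. The visit windows (Visit 6 ± 1 day, Visit 7 ± 7 days; Protocol 9.2.1.8 and 9.2.1.9) allow 76 to 92 days, so 1/76 = 1.3% to 1/92 = 1.1%. After two periods it is 1/168 = 0.6%.

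**2. Bleeds.** Assume two bleeds on the old dose before the escalation day. Old-dose rate:

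| Escalation day | As written | Split at the injection (4.5.2) | Old dose ended the day before |
|---|---|---|---|
| No bleed | 2 × 365.25/85 = 8.59 | 2 × 365.25/84 = 8.70 | 8.70 |
| One bleed before the injection | 3 × 365.25/85 = 12.89 | 3 × 365.25/84 = 13.04 | 8.70 |
| One bleed after the injection | 12.89 | 8.70 | 8.70 |

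As written, a bleed on that day also adds 365.25/78 = 4.68 to the new-dose rate, whichever side of the injection it fell on. If it came after the injection, the old-dose rate is too high by 12.89 − 8.70 = 4.19, or 4.19/8 = 0.52 in a mean over eight subjects. If it came before, the old-dose rate is nearly right and the new-dose rate carries the surplus.

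**3. How often.** With a constant Poisson rate (assumed), the chance of a bleed on a given day is 1 − exp(−rate/365.25): 1.1%, 2.2% and 3.2% at 4, 8 and 12 bleeds a year. Usually only the 1.2% applies.

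**4. Part A to Part B.** If the end of Part A is taken from section 4.5.2, it normally falls on the Visit 6 date. A whole-day formula would then count that date in both parts for every subject who enters Part B. This depends on a definition that the Additional SAP does not give.

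**5. Rows by dose initially given.** Assume three bleeds in an 84-day Part A, escalation at Visit 6, and a last dose 77 days later, so 84 + 77 + 1 = 162 days. The main SAP rate on the dose initially received is 3 × 365.25/84 = 13.04. The combined row gives 3 × 365.25/162 = 6.76 with no later bleed, 4 × 365.25/162 = 9.02 with one, and 6 × 365.25/162 = 13.53 with three. The two quantities answer different questions, and the row needs a label that says which it is.

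**The case against.** The strongest reply is that the sentence is incomplete, and if the missing words are 'before' rather than 'of', there is no overlap. Double counting of a bleed is also inferred from silence: onset times are recorded in the diary (Protocol 9.4.1), and the programming follows reference SAS code that a reader cannot see. That uncertainty stands for the bleeds. For the days, the next sentence of the Additional SAP supports the natural reading, and an ambiguous end date needs correcting in any case.

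The reply is also right about size, and several stronger inferences are not supported.

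- *The published rates by dose are materially wrong.* The documents do not say how many subjects escalated at Visit 7 or later, and the usual effect is about 1% of one subject's denominator. The 4.19 applies only when a bleed follows the injection on that day.
- *The old dose should simply end the day before.* Subjects attend these visits before their injection (Protocol 9.2.1.8 to 9.2.1.10), so a bleed earlier that day occurred on the old dose. That rule would give 8.70 where the 4.5.2 timing gives 13.04, a third lower (4.34/13.04), and would credit the bleed to the new dose.
- *A subject escalated at Visit 6 gets a one-day old-dose window, where one bleed gives 365.25.* This requires giving such a subject Part B time on the old dose, although section 4.5.2 makes the Visit 6 injection the first of Part B.
- *The rows by dose initially given are wrong or hide escalated time.* A summary by starting cohort is legitimate, and the text does say that it covers the whole study and any study drug. Nor is the window cut at escalation less biased. In a simulation with assumed inputs (gamma-Poisson bleeds with shape 2, true rate 8, 84 + 84 days, no dose effect, 50% to 100% of bleeds counting towards escalation), the whole-study window returned 8.0. The cut window returned 8.4 to 8.8 as a mean of subject rates, or 7.6 down to 7.2 pooled. Escalation depends on bleeds, as SAP section 6.2.1 itself warns.

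**Conclusion.** The point holds as a minor correction. Read naturally, the rule for dose actually given counts one day too many for each escalation within Part B, and it leaves a bleed on that day open to being counted under both doses. The conclusion rests on reading the incomplete sentence as the day of escalation, and on the Additional SAP not importing the period limits of section 4.5.2. The Part A and Part B overlap is conditional on how the end of Part A is defined. The rows by dose initially given raise only a question of labelling. The table is descriptive and post hoc, and nothing here touches the primary safety analysis.

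**What to change.** - Complete the sentence, and apply the date-and-time split of SAP section 4.5.2 to the windows for dose actually given, at whichever visit the higher dose is first injected. Time and bleeds before that injection belong to the old dose; those from the injection onward belong to the new one. With elapsed time in days, the added day is dropped.
- Use the same split at the Visit 6 injection for Part A and Part B. State that a subject escalated at Visit 6 has no Part B time on the old dose.
- If whole days are kept, count the boundary day in one denominator only, and allocate a bleed on that day by its recorded time relative to the injection. Give a convention for a missing time.
- As presentation, insert the missing word 'last' before the intake of study drug. Label the combined and Part B rows by dose initially given as by starting cohort, including time on an escalated dose.

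The cost is one changed derivation, one definition and two labels. Section 4.5.2 already relies on injection times and the diary collects bleed onset times, so no new data are needed.
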